#### Computerized therapy

Participants undergoing computerized therapy will undergo initial assessments to establish their therapy objectives and subsequently determine the most appropriate application. Studies have indicated that the use of speech therapy apps can result in enhancements in language proficiency, confidence in communication, and overall quality of life among individuals with aphasia (Stark et al., 2015; Palmer et al., 2019). Furthermore, speech therapy apps and digital interventions have demonstrated potential in aiding individuals with dementia, particularly in enhancing language skills, mood regulation, and cognitive function (Lanza et al., 2021). These apps often incorporate features targeting diverse language domains, memory enhancement exercises, and functional activities. For individuals choosing to integrate cognitive behavioral therapy (CBT) into their speech or cognitive therapy regimen, we offer a structured framework focusing on cognitive restructuring, relaxation techniques, behavioral activation, problem-solving skills, gratitude exercises, and more. These interventions are designed to facilitate their progress during the computerized therapy phase (Bilbrey et al. 2022).

Cognitive training exercises have been drawn from the computer aided cognitive training programs including BrainHQ (Posit Science, 2015), Tactus Therapy, and Constant Therapy. The efficacy of these tasks has been demonstrated for behavioral performance on a wide of variety cognitive tasks in clinical populations(Anderson et al., 2013), older adults ((Boggio et al., 2006, 2007; Fregni et al., 2006; Kang et al., 2009, Smith et al., 2009; Tennstedt & Unverzagt, 2013), and healthy individuals ((Roenker et al., 2003)). Improvements in behavioral performance have also been shown to be accompanied by changes in cortical, functional activity ((Berry et al., 2010; Rosen et al., 2011; Scalf et al., 2007). During each of the cognitive training sessions, patients will perform 4 tasks selected from the BrainHQ exercise series, designed to target processing speed and executive functions such as shifting, updating, monitoring, and manipulation. The combined tasks will take approximately 40 minutes to complete.

#### Assessment

Follow-up assessment will probe all sets of trained phoneme-grapheme correspondences, words, or other stimuli (e.g. sentences) to identify whether or not the patient has retained knowledge of the trained items. We will look at generalization effects (i.e. effects of training to untrained items). Differences in baseline measures in pre- and post-therapy accuracy for phoneme-grapheme correspondences for each patient will be evaluated using chi-square or Fisher's exact tests.

Participants will receive approximately 3-5 therapy sessions per week for 1-3 weeks for each stimulation site. There will be 1-5 stimulation sites depending on the characteristics of each individuals and their availability.

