#### Spelling

#### Treatment of the PGC mechanism (PGC intervention)

For the PGC intervention, patients will receive language therapy of either phoneme-grapheme correspondence (PGC) or study of particular words (lexical therapy) or other similar type of therapy depending on the particular spelling deficit of each patient. Up to 30 English sounds will be selected representing most common word-initial English phonemes (speech sounds). Then a set of up to 30 English words starting with these sounds will be used as prompts to help the participants relate each sound to a grapheme (abstract letter identity or sequence of letter identities). In the case of spelling therapy with words, sets of up to 50 English words with matched psycholinguistic characteristics (frequency, length etc) will be chosen and divided in sets for either baseline testing, training, homework, or repetition. In the case of PGC therapy, the participant will be either asked to provide the letters that would correspond to each sound and if failed to do so will be provided with word prompts. In the case of lexical therapy, the participant will be asked to spell the chosen words and if failed to do so will be taught the spelling of each word in the training set or proceed to the rest of the set in other sets. Words or PGCs will be taught in blocks of 10; when the patient reaches criterion (80% correct) he or she will continue to the other blocks. Individuals who reach criterion quickly will move to a second stage, in which they will be asked to write words beginning with each target phoneme. They will be assisted in correcting the spelling of the words by "sounding out" the word. Baseline evaluation before each therapy session will be held before each therapy session and will either require that the participant would choose--from a series of possible initial letters or letter sequences of English written in front of him or her--the letter or letter sequence that corresponds to the phoneme the examiner provides each time. Treatment of the lexical access mechanism (lexical access intervention).

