For the lexical access treatment we will follow the methodology of the only other published spelling intervention in PPA (Rapp & Glucroft, 2009). Stimuli will consist of three word sets (n=10 for each set) that will be matched for lexical frequency, letter length, regularity, and concreteness. We will use 10 stimuli for each set to better match the PGC and lexical treatments. Set 1 will serve as trained items for the first condition (either sham or tDCS), and set 2 as untrained items and then set 2 will serve as trained items JHMIRB eFormA 01

and set 3 as untrained. A spell-study-spell procedure (Beeson et al., 2013; Rapp & Glucroft, 2009) similar to that used in a number of other studies will be applied to the trained words, such that at every training session the patient will be asked: (1) to spell each word to dictation, (2) to study the word presented on a written note card and orally name each of its letters while the experimenter repeats the word, and (3) if the word has been spelled incorrectly to attempt to spell it again. This procedure will be repeated until the words of each set are correctly spelled for two consecutive sessions. If a word is spelled correctly on the first attempt, the word will still be presented for the participant to study and only then will the experimenter continue to the next word. Untrained words will be presented for spelling to dictation only at the time of the pre- and post-treatment evaluations and at two follow-ups to evaluate whether therapy gains generalize to the spelling of other words.

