#### 6. Study Statistics

#### *a. Primary outcome variable.*

The primary outcome measures will be: a) change in performance from pre- to post-treatment levels on the trained items (e.g. change in % accuracy in phoneme-grapheme conversion of trained phonemes, % accuracy naming of trained pictures, average % correct names produced in trained categories in 1 minute), and, b) generalization to untrained items, measured by change in performance from pre- to post-treatment levels on the trained items (e.g. change in % accuracy in phoneme-grapheme conversion of untrained phonemes, % accuracy naming of untrained pictures, average % correct names produced in untrained categories in 1 minute). For those individuals with DLPFC stimulation for executive functions, we will use an additional automated score from BrainHQ program training (Smith et al., 2009). For individuals

receiving home-based tDCS over the left perisylvian areas and their right hemisphere homologs, we will assess pre- to post- language scores.

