## c. Statistical plan including sample size justification and interim data analysis.

Design. This is a crossover trial, where each participant will be randomly assigned to receive either "IFG tDCS, then sham then SMG (in case a second stimulation site is implemented)" (group1) or "SMG then sham then IFG" or "sham then IFG then SMG". In case a second stimulation site is not implemented participants will receive either sham and then tDCS (group 1) or tDCS and then sham (group 2). Based on previous studies regarding long-term effects of tDCS (see Fiori et al., 2011; Fridriksson et al., 2011; both looking at 3-weeks post-stimulation in participants with aphasia) and given the degenerative nature of PPA (and some cases of MCI), we assume that even though the effect of tDCS on the absolute level of the outcome may or may not persist at 2 weeks, the effect on the rate of decline persists no longer than 2 weeks. Analyses. The primary analyses will be a robust type of repeated measures Multivariate ANCOVA. Specifically, for each subject (i) and at follow-up times t=immediately after treatment, then 2 weeks and 2 months, we will consider the data  $IFG_{ti}$ ,  $SMG_{ti}$ , and  $S_{ti}$ ; here,  $IFG_{ti}$  is the change of outcome from just before IFG tDCS treatment to time t after IFG tDCS treatment for subject i; and similarly for SMGt,i, and St,i for IFG tDCS and sham. For the behavioral methods, change of outcome is considered the difference (before and after therapy) of the independent measure of initial letter-sound associations learned. Then the research hypothesis that IFG (or SMG) treatment is superior to sham will be tested by testing the hypotheses that the distribution  $pr(R_{ij} - S_{t,i})$  (or  $pr(L_{t,i} - S_{t,i})$ ) is not centered at zero. This will be done nonparametrically by obtaining the latter null distributions by the random permutation of the treatment labels (IFG, S, SMG) of the data for each patient (Rosenbaum, 1988). The design effect, i.e., the ratio of sample sizes needed by an independence design vs. the crossover design to achieve a given power, depends on the correlations of outcomes across times and treatments. We have calculated that this crossover design with 30 participants and design effect of 1.5 has power 75% to detect an effect size of 0.8 between a tDCS site and sham treatment. In secondary analysis, we will use regression to examine if any effects of tDCS vary across participants with different characteristics such as age and atrophy volume. The present design allows us to evaluate the language and neuromodulatory effects of both IFG and SMG stimulation as well as language therapy alone (in the condition of sham stimulation).

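### Each patient's pre- and post-therapy phoneme-grapheme accuracy is compared with tests for independent samples, although the same items are probed twice

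*Combined protocol and SAP*

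**What the plan says.** Section 3a of the combined protocol and SAP, under Assessment, states how change is tested within a patient: differences in "pre- and post-therapy accuracy for phoneme-grapheme correspondences for each patient will be evaluated using chi-square or Fisher's exact tests". The same paragraph says that "Follow-up assessment will probe all sets of trained phoneme-grapheme correspondences, words, or other stimuli". The items are a chosen set: under the PGC intervention, "Up to 30 English sounds will be selected representing most common word-initial English phonemes", taught in blocks of 10. Section 6a scores the outcome as "change in % accuracy in phoneme-grapheme conversion of trained phonemes".

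The pre-therapy reference is not fixed, because the PGC section says "Baseline evaluation before each therapy session will be held before each therapy session". No section names McNemar's test or any other paired or item-level method for this comparison. The comparison of tDCS with sham in section 6c is a separate analysis. It works on within-patient change scores and uses "random permutation of the treatment labels (IFG, S, SMG) of the data for each patient".

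**The concern.** In a single patient's table the sampling unit is the item. Each trained phoneme gives one result before therapy and one after, so every item contributes a pair. A chi-square or Fisher test on the pre-by-post table treats the two probes as separate sets of items and discards which items were gained and which were lost.

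A phoneme that a patient knows before therapy will usually still be known afterwards, so the two results should be positively correlated. The difference in accuracy then varies less than the unpaired tests assume. Their p-values are too large, and a patient with a moderate real gain may show no significant change. The error does not create false positives.

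**Working it through.** **The plan's own figure.** The only power figure in the documents is in section 6c: 75% with 30 participants, design effect 1.5 and effect size 0.8. Alpha is not stated; I take two-sided 0.05. The equivalent parallel design has 30 × 1.5 = 45 participants, or 22.5 per arm. The noncentrality is 0.8 × √(22.5/2) = 2.683. The normal approximation gives Φ(2.683 − 1.960) = 76.5%, and the noncentral t with 43 degrees of freedom gives 74.6%. The figure reproduces. It belongs to the tDCS-versus-sham comparison and does not depend on the per-patient test.

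**Model for one patient.** Let p be the proportion of items known before therapy, g the proportion of unknown items gained, and l the proportion of known items lost. Each of n items falls into one of four cells:

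- kept: p(1 − l)
- lost: pl
- gained: (1 − p)g
- still unknown: (1 − p)(1 − g)

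The number of items comes from the documents (up to 30, in blocks of 10). The values of p, g and l are assumptions.

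**Why the unpaired tests go wrong.** Take p = 0.40, g = 0.45, l = 0.05.

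- Post-therapy accuracy is 0.38 + 0.27 = 0.65.
- The unpaired variance of the difference, times n, is 0.40 × 0.60 + 0.65 × 0.35 = 0.4675.
- The covariance is 0.38 − 0.40 × 0.65 = 0.12, a correlation of 0.51.
- The true variance, times n, is 0.4675 − 2 × 0.12 = 0.2275.
- The unpaired standard error is therefore too large by a factor √(0.4675/0.2275) = 1.43.

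**Power.** Exact multinomial enumeration, two-sided 0.05, chi-square without continuity correction:

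| Items | Known before → after | l | Correlation | Fisher | Chi-square | Exact McNemar | Mid-p McNemar |
|---|---|---|---|---|---|---|---|
| 30 | 40% → 65% | 5% | 0.51 | 34.8% | 49.4% | 68.9% | 79.5% |
| 20 | 40% → 65% | 5% | 0.51 | 15.3% | 26.7% | 35.9% | 52.6% |
| 10 | 40% → 65% | 5% | 0.51 | 3.1% | 9.9% | 2.6% | 9.2% |
| 30 | 40% → 55% | 30% | 0.25 | 11.4% | 18.3% | 17.1% | 23.8% |
| 30 | 40% → 56% | 5% | 0.64 | 5.8% | 12.1% | 31.5% | 46.2% |
| 30 | 50% → 80% | 5% | 0.38 | 61.8% | 73.7% | 80.7% | 87.8% |
| 30 | 40% → 80% | 5% | 0.31 | 89.7% | 94.5% | 96.1% | 97.9% |
| 30 | 30% → 80% | 5% | 0.25 | 98.7% | 99.5% | 99.6% | 99.8% |

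**No true change.** With 30 items, 50% known at both probes and correlation 0.5, the rejection rates at a nominal 5% are Fisher 0.2%, chi-square 0.6%, exact McNemar 1.8% and mid-p McNemar 3.7%. Over 15 no-change settings the largest mid-p rate was 4.7%. At zero correlation chi-square holds its level (5.2%), so the fault depends on the pairing being informative.

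**One observed result.** For 12/30 before and 19/30 after, Fisher gives p = 0.120 and chi-square p = 0.071, whatever happened item by item. The paired tests separate the cases:

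| Gained | Lost | Exact McNemar | Mid-p McNemar |
|---|---|---|---|
| 7 | 0 | 0.016 | 0.008 |
| 8 | 1 | 0.039 | 0.021 |
| 9 | 2 | 0.065 | 0.039 |
| 10 | 3 | 0.092 | 0.057 |

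**Small sets.** With every change in the same direction, exact McNemar gives 2 × 0.5⁵ = 0.063 for five changed items and 2 × 0.5⁶ = 0.031 for six. It therefore cannot reach 0.05 with fewer than six changes. Mid-p gives 0.031 for five.

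**The case against.** **No decision rests on this test.** The sentence stands in a procedures section with no alpha level, responder rule or hypothesis attached, and the group comparison is unaffected. This stands, and it limits the weight of the point. It does not make the named test suitable for the data.

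**The size is assumed.** The PGC section trains each block to 80% correct, so patients who reach that criterion from a low start show large gains. From 30% to 80% the tests hardly differ (98.7% to 99.8%). This stands for those patients. From 50% to 80%, however, Fisher has 62% power and chi-square 74%, against 81% and 88% for exact and mid-p McNemar, and not every patient will reach criterion.

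**Fisher is the worse of the two planned tests.** This is also right. In the 40% to 65% setting with 30 items, chi-square loses 20 points against exact McNemar where Fisher loses 34. With correlation 0.25, chi-square slightly exceeds exact McNemar (18.3% against 17.1%).

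**At 10 items the change buys no power over chi-square.** In the setting above chi-square has 9.9% and mid-p 9.2%. The benefit appears at 20 to 30 items. The small sets are a reason to prefer mid-p to exact McNemar, not evidence that pairing helps there.

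**The wording could mean McNemar, which is a chi-square test.** The sentence is loosely written and describes no table, and one response per item per probe is inferred. But Fisher's exact test, offered as the alternative, is not a paired test, so the unpaired reading is the natural one. If McNemar was meant, it needs to be named.

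**Conclusion.** The point holds. The plan names independent-sample tests for data that are matched by item, and no section supplies a paired alternative.

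In the 30-item settings tabulated, Fisher loses between about 1 and 34 percentage points of power against exact McNemar. Chi-square ranges from about 1 point better to 20 points worse. The loss is largest for moderate gains with well-retained items and close to nothing for very large gains. These sizes rest on assumed gain and loss rates, positive item correlation, one response per item per probe, and two-sided 0.05, because the documents give none of these.

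The error is conservative and limited to per-patient reporting. It should be corrected, but it does not threaten the trial's main comparison.

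**What to change.** In section 3a, Assessment, replace the chi-square or Fisher tests with wording such as: *For each patient, change in phoneme-grapheme accuracy will be tested with a McNemar mid-p test on the number of items gained versus lost between the pre-therapy and post-therapy probes.*

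Add a sentence that states:

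- which pre-therapy probe enters the table, given that there is a baseline before every session;
- that the item-level response at each of the two probes is retained.

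The cost is one or two sentences. The documents describe item testing and accuracy scores but do not say that item-level responses are stored, so this must be confirmed. No additional visit, test or participant is needed.

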#### tDCS methods:

Participants will take part in 5-15 consecutive training sessions (3-5 per week), each with a different tDCS condition/site of stimulation (see Table 1) separated by 2 months. Three pre-training sessions separated by 2 weeks, each with a different tDCS condition/site of stimulation (see Table 1), may be proposed to pre-test the tDCS montages. Anodal tDCS has typically been shown to up-regulate neuronal excitability and produce enhancement of behavioral performance. We hypothesize that anodal cerebral tDCS applied during behavioral therapy will enhance the therapeutic outcome relative to the sham tDCS condition as measured by the change from pre- to post-treatment accuracy in the trained task (e.g. number of correctly learned grapheme-phoneme correspondences, correctly named pictures, correctly named words in a given category) for trained and untrained stimuli. Previous tDCS protocols for acquisition of eyeblink

conditioning using tDCS have received Johns Hopkins IRB approval. We will use either the same equipment as [name] and his team have used (a Chattanooga lonto Device) as well as the same application technique, recently acquired state-of-the-art device using special software for doubleblinding (Soterix 1x1 CT: clinical trials), or a Neuroelectrics Starstim 8 device, which is a high-definition tDCS cap with higher precision. In order to administer intervention during the global pandemic and in a virtual manner, we will offer the option of remote stimulation (Soterix mini-CT device and MIND STIM+, YBrain). Attached please find letters from Clinical Engineering documenting that the tDCS devices have undergone clinical inspection as well as the manuals. When remote devices are implemented, participants and spouses will be trained prior to intervention and sessions will be conducted in real-time via video conference (e.g., Zoom). Stimulation will be delivered at an intensity of 1-2mA (estimated current density 0.04 mA/cm2; estimated total charge 0.048C/cm2) for a maximum of 20 minutes in the tDCS groups and for a maximum of 30 seconds in the Sham group. For both interventions (tDCS and Sham) the electrical current will be increased in a ramp-like fashion at the onset of the stimulation eliciting a transient tingling sensation on the scalp that usually disappears over seconds. Although the ramping process requires the researcher's input, it is now feasible to blind study staff who will be applying tDCS, as well as participants, as we now have a box that allows another member of the team to set the box to "tDCS" or "sham" without the knowledge of the researcher providing the therapy. In the Starstim 8 and remote devices, double-blinding is achieved through codes known only to the PI who is not administering any stimulation or evaluation, so both the technician or professional who administers the stimulation and evaluation are blind to the current condition being either actual tDCS or sham. After the ramping, in the sham condition, the intensity drops to 0 mA. These procedures have been shown to successfully blind participants as to whether they were members of experimental or control groups (Gandiga et al., 2006). The sites of tDCS application will be determined by the type of therapy used and the PPA variant group or MCI and will be either the inferior frontal gyrus (IFG), the supramarginal gyrus (SMG), or the middle temporal gyrus (MTG) or a combination as shown in the literature. A recent meta-analysis of the functional neuroimaging literature on spelling has not yet identified clearly the neural substrates for PG conversion; the most plausible network includes the inferior parietal lobule including the supramarginal gyrus (Purcell et al., 2011). This area has also been identified as a critical area for spelling in the lesion literature as well. Another plausible area that shows activations during both PG conversion and lexical (word) spelling is the inferior frontal gyrus (IFG) (Purcell et al., 2011) and lesions in the IFG are associated with impaired PG conversion (Beeson et al., 2010). The stimulation site of IFG will be determined between F7 and F8 electrodes and that of SMG between TP3 and TP4 using the EEG 10-20 electrode position system (Homan, 1988). Additionally, studies have reported positive results of tDCS over the left dorsolateral prefrontal cortex (DLPFC) leading to improvement in attention deficits due to stroke, Parkinson's disease, and major depression (Boggio et al., 2006, 2007; Fregni et al., 2006; Kang et al., 2009). In addition to improving attention, anodal tDCS at the left DLPFC has been shown to improve working memory in TBI patients (Ulam et al., 2015). We hypothesize that anodal tDCS over the L DLPFC when administered in combination with cognitive training will improve language performance of PPA and MCI participants more than behavioral therapy alone, and that improvements may generalize to some other cognitive functions. The dependent variable will be the same baseline and post-therapy evaluation as described above that will take place before, after, 2 weeks and 2 months post-stimulation for each stimulation condition (see Table 1). These same areas, predominantly on the left, are activated during naming (Jarso et al., 2013) and working memory (Philipose et al., 2007). In most cases of PPA and all cases of MCI, we will stimulate areas of the left hemisphere that are not atrophied. In the most advanced cases of PPA, with severe left hemisphere atrophy, we will stimulate the same sites in the right hemisphere in order to stimulate its compensatory mechanisms (see Hypothesis 1d). By this design we will be able to achieve a within-subject design for all conditions as well as to evaluate immediate, short- and long-term effects of each stimulation site without confounds and without any carry-over effects. We will also conduct a 6-month language evaluation to assess the overall therapy gains.
